9.9 Additional Research

Not applicable per Protocol Amendment 01. The following information refers to the original study design.

This protocol will include both sample collection and residual sample storage for additional research (AR).

For All US sites:

Additional research is required for all study participants, except where prohibited by IRBs/ethics committees, prohibited by local laws or regulations, or academic/institutional requirements. Where one or more of these exceptions occurs, participation in the additional research should be encouraged but will not be a condition of overall study participation.

- If the IRB/ethics committees and site agree to the mandatory additional research retention and/or collection, then the study participant must agree to the mandatory additional research as a requirement for inclusion in the study.
- If optional participation is permitted and approved, then the study participants may opt out of the additional research retention and/or collection.

For non-US Sites:

Additional research is optional for all study participants, except where retention and/or collection is prohibited by local laws or regulations, ethics committees, or institutional requirements.

Additional research is intended to expand the R&D capability at Bristol-Myers Squibb, and will support as yet undefined research aims that will advance our understanding of disease and options for treatment. This may also include genetic/genomic exploration aimed at exploring disease pathways, progression, and response to treatment etc.

Sample Collection and Storage

Residual PK, immunogenicity, blood (or blood derivatives) or tumor tissue (recent, archival, or fresh biopsy and extracted RNA/deoxyribonucleic acid [DNA]) from tumor biopsy and biomarker collections (see Table 9.9-1 below) will also be retained for additional research purposes.

Samples kept for future research will be stored at the BMS Biorepository in New Jersey, USA or an independent, BMS-approved storage vendor.

The manager of these samples will ensure they are properly used throughout their usable life and will destroy the samples at the end of the scheduled storage period, no longer than fifteen (15) years after the end of the study or the maximum allowed by applicable law.

Transfers of samples by research sponsor to third parties will be subject to the recipient's agreement to establish similar storage procedures.

Samples will be stored in a coded fashion, and no researcher will have access to the key. The key is securely held by the Investigator at the clinical site, so there is no direct ability for a researcher to connect a sample to a specific individual.

Further details of sample collection and processing will be provided to the site in the procedure manual.

Table 9.9-1: Residual Sample Retention for Additional Research Schedule

Sample Type	Time points for which residual samples will be retained
PK	All
Immunogenicity	All
Serum	All
Tumor Biopsy	All
Isolated DNA/RNA	All
Whole blood DNA	All

Abbreviations: DNA, deoxyribonucleic acid; PK, pharmacokinetics; RNA, ribonucleic acid.

9.10 Other Assessments

9.10.1 *Investigational Site Training*

BMS will provide quality investigational staff training prior to study initiation. Training topics will include but are not limited to Good Clinical Practice, AE reporting, [REDACTED] [REDACTED] study details and procedures, eCRFs, study documentation, informed consent, and enrollment of WOCBP.

9.11 Health Economics OR Medical Resource Utilization and Health Economics

Not applicable per Protocol Amendment 01. The following information refers to the original study design.

Healthcare Resource Use data associated with medical encounters will be collected in the CRF by the investigator and study-site personnel for all participants throughout the study. Protocol-mandated procedures, tests, and encounters are excluded.

The data collected may be used to conduct exploratory economic analyses and will include the following:

- Number and duration of medical care encounters, including surgeries, and other selected procedures (inpatient and outpatient)
- Duration of hospitalization (total days length of stay, including duration by wards; eg, intensive care unit)
- Number and character of diagnostic and therapeutic tests and procedures
- Outpatient medical encounters and treatments (including physician or emergency room visits, tests and procedures, and medications)

10 STATISTICAL CONSIDERATIONS

Per Protocol Amendment 01, only safety analyses will be conducted. Summary tables and listings for baseline characteristics, disposition, safety, and efficacy data will be provided to support the Clinical Study Report (CSR). Additional summaries (as appropriate for small sample size) will be planned in the SAP to support study data disclosure on original study objectives.

10.1 Statistical Hypotheses

Not applicable per Protocol Amendment 01. The following information refers to the original study design.

Part 1 of the study will be subjected to statistical hypothesis testing.

Research Hypothesis (Part 1 - Randomized Study)

Nivolumab exposures following [REDACTED] (BMS-986298) 600 mg administered Q2W are non-inferior to exposures following nivolumab (BMS-936558) 240 mg IV Q2W for the adjuvant treatment of melanoma.

10.2 Sample Size Determination

The aim of the study is to assess the safety and tolerability of [REDACTED] and Nivo IV. This has changed from the original protocol's study objective of PK. Sample size calculations are not based on statistical considerations. There were 14 participants randomized and treated at the time of Protocol Amendment 01.

10.3 Analysis Sets

For the purposes of analysis, the following populations are defined:

Population	Description
All Enrolled Participants	All participants who signed an ICF and are registered into the IRT. This is the primary dataset for disposition.
All Randomized Participants	All participants who are randomized to any treatment group. This is the primary dataset for analyses of demography, protocol deviations, baseline characteristics, efficacy, and outcome research for the randomized part of the study.
All Treated Participants	All participants who receive at least 1 dose of nivolumab. This is the primary dataset for dosing and safety analyses. Data will be analyzed based on randomized treatment, except if a participant received the same incorrect treatment throughout the study, then the participant will be analyzed based on treatment received.

Abbreviations: ICF, informed consent form; IRT, interactive response technology.

10.4 Statistical Analyses

The SAP will be finalized prior to primary endpoint database lock (DBL), and it will include a more technical and detailed description of the statistical analyses described in this section. This section is a summary of the planned statistical analyses of the most important endpoints, including the primary endpoint.

A description of the participant population will be included in the clinical study report, including subgroups of age, gender, race and other study specific populations and demographic characteristics. A description of participant disposition will also be included in the clinical study report.

10.4.1 General Considerations

A summary of the planned statistical analysis is described below in subsequent paragraphs.

10.4.2 Primary Endpoint(s)

Safety is the primary endpoint. See [Table 10.4.2-1](#) for details.

Table 10.4.2-1: Primary Endpoint

Primary Endpoint	Description	Timeframe

 • AEs/SAEs, treatment-related AEs/SAEs for each treatment group. 	
 • Incidence of all AEs/SAEs, treatment-related AEs/SAEs for each treatment group. 	
 • Up to 100 days after the last treatment of study intervention or up to discontinuation of study treatment.

Abbreviations: AE, adverse event; IMAE, immune-mediated adverse event; SAE, serious adverse event.

All safety analyses will be performed using the All Treated participants population.

The frequency of AEs, SAEs, and treatment-related AEs/SAEs will be tabulated by treatment arm. IMAEs, AEs, and SAEs leading to discontinuation of study drug, infusion/injection-related AEs, [REDACTED] deaths, and abnormalities in specific clinical laboratory assessments will be presented as listings by treatment arm.

The safety summary will be presented by severity where applicable. Analyses will be conducted using the 30 and/or 100-day safety window from the day of last dose received. AEs will be coded using the most recent Medical Dictionary for Regulatory Activities (MedDRA) version available during the conduct of the study. AEs and laboratory values will be graded for severity according to the NCI CTCAE version 5.0.

10.4.2.1 Part 1 PK Co-Primary Endpoints

Not applicable per Protocol Amendment 01. The following information refers to the original study design.

[figure not shown]
Table 10.4.2.1-1: Part 1 PK Co-Primary Endpoint

Co-Primary Endpoint	Description	Timeframe
Cavgd28	Time averaged nivolumab serum concentration over the first 28 days	First 28 days of treatment
Cminss	Minimum nivolumab serum concentration at steady-state	17 weeks after the start of treatment

Abbreviations: Cavgd28, time averaged nivolumab serum concentration over the first 28 days; Cminss, minimum nivolumab serum concentration at steady-state, PK, pharmacokinetics.

For Primary PK Endpoints analysis, a linear fixed effect model with treatment and stratification factors (defined in the study design) as fixed effects will be fitted to the log-transformed Cavgd28 and Cminss for use in estimation of treatment effects and construction of CIs. To assess non-inferiority of [REDACTED] to Nivo IV, point estimate and the 2-sided 90% CIs for treatment differences on the log scale will be exponentiated to obtain estimates for ratio of geometric means and respective 90% CIs for Cavgd28 and Cminss on the original scale.

Non-inferiority of [REDACTED] to Nivo IV will be concluded if the lower limit of the 2-sided 90% CIs for the ratio of geometric means for nivolumab Cavgd28 and Cminss is not lower than 0.8.

10.4.3 Secondary Endpoint(s)

Per Protocol Amendment 01, secondary endpoints [REDACTED] of the study have been removed. Efficacy, patient-reported outcomes (PROs), and biomarker analyses will not be completed. Samples already collected for PK and immunogenicity assessments will be analyzed bioanalytically for nivolumab concentrations and anti-drug antibodies (ADAs) and reported as listings. Further collections for PK, ADAs, biomarkers, and PROs will be discontinued. The following information refers to the original study design.

10.4.3.1 Part 1 Secondary Endpoint(s)

Not applicable per Protocol Amendment 01. The following information refers to the original study design.

Table 10.4.3.1-1: Part 1 Secondary Endpoints

Secondary Endpoints	Description	Timeframe
Key Secondary		
Incidence of all AEs/SAEs, treatment-related AEs, including IMAEs, SAEs, AEs [REDACTED] [REDACTED] leading to discontinuation or death, and laboratory abnormalities for each treatment group	Incidence of all AEs/SAEs, treatment-related AEs, including IMAEs, SAEs, AEs [REDACTED] [REDACTED] leading to discontinuation or death, and laboratory abnormalities for each treatment group	Up to 100 days after the last treatment of study intervention or up to discontinuation of study treatment
OS rate	Time from randomization to death due to any cause	Until death, up to 36 months
RFS (per investigator) rate	Time between the date of randomization and the date of first recurrence (local, regional, or distant metastasis), new primary melanoma, or death (whatever the cause), whichever occurs first	Until recurrence event, up to minimum follow-up of 12 months from last participant randomized in the study or death whichever is earlier

Table 10.4.3.1-1: Part 1 Secondary Endpoints

Secondary Endpoints	Description	Timeframe
Other Secondary		
Cmind28; Cmax1, Tmax, Cmaxss, and Cavgss	Minimum nivolumab serum concentration at Day 28; maximum nivolumab serum concentration after the first dose; time of maximum nivolumab serum concentration after the first dose; maximum nivolumab serum concentration at steady-state; time-averaged nivolumab serum concentration at steady-state	First 28 days of treatment; 17 weeks after the start of treatment
Percentage of participants who develop anti-nivolumab antibodies and neutralizing antibodies, if applicable, and the impact of anti-nivolumab antibodies on AEs, administration-related reactions, and events within MedDRA SMQ Anaphylactic reactions	Percentage of participants who develop anti-nivolumab antibodies and neutralizing antibodies, if applicable, and the impact of anti-nivolumab antibodies on AEs, administration-related reactions, and events within MedDRA SMQ Anaphylactic reactions	Up to 100 days after the last study treatment or up to discontinuation of study treatment
Mean CTSQ Satisfaction domain scores and score change from baseline at each assessment time point	Mean CTSQ Satisfaction domain scores and score change from baseline at each assessment time point	At each assessment time point

Abbreviations: AE, adverse event; Cavgss, time-averaged nivolumab serum concentration at steady-state; Cmax1, maximum nivolumab serum concentration after the first dose; Cmaxss, maximum nivolumab serum concentration at steady-state; Cmind28, minimum nivolumab serum concentration on Day 28; CTSQ, Cancer Treatment Satisfaction Questionnaire; IMAE, immune mediated-adverse event; MedDRA, Medical Dictionary for Regulatory Activities; OS, overall survival; RFS, recurrence-free survival; SAE, serious adverse event; SMQ, standard MedDRA query; Tmax, time to maximum nivolumab serum concentration after the first dose.

The ratio of geometric means and its 90% CI of the relevant secondary PK endpoints of Cmind28, Cmax1, Cmaxss, and Cavgss endpoints will also be tabulated similar to the PK primary endpoint but will not be used for concluding non-inferiority. Medians and ranges will be presented for Tmax by treatment group. Summary statistics by treatment group will be provided for each nivolumab PK parameter together with subject listing. Geometric means and coefficients of variation will be presented by treatment group together with N, mean, SD, median, minimum, and maximum.

Safety, immunogenicity, biomarkers, outcome research, and efficacy endpoints will be analyzed descriptively.

RFS will be programmatically determined based on the disease recurrence date provided by the investigator and is defined as the time between the date of randomization and the date of first recurrence (local, regional, or distant metastasis), new primary melanoma (including melanoma in situ), or death (whatever the cause), whichever occurs first. A participant who dies without reported recurrence will be considered to have recurred on the date of death. For participants who remain alive and whose disease has not recurred, RFS will be censored on the date of last evaluable disease assessment. For those participants who remain alive and have no recorded post-

randomization disease assessment, RFS will be censored on the day of randomization. Censoring rules are presented in Table 10.4.3.1-2 below.

Table 10.4.3.1-2: Censoring Scheme for Primary Definition of Recurrence-Free Survival

Situation	Date of Event or Censoring	Outcome
Recurrence (local, regional, distant, new primary melanoma, including melanoma in situ)	Date of first recurrence	Event
Death without recurrence	Date of death	Event
No baseline disease assessment	Date of randomization	Censored
No on-study disease assessments and no death	Date of randomization	Censored
No recurrence and no death	Date of last evaluable disease assessment	Censored
Second non-melanoma primary cancer (excluding BCC and/or SCC) reported prior or on the same day of disease assessment	Date of last evaluable disease assessment prior to or on the same date of diagnosis of second non-melanoma primary cancer	Censored

Abbreviations: BCC, basal cell carcinoma; SCC, squamous cell carcinoma.

In Part 1, RFS distributions will be descriptively compared between treatment groups and hazard ratios, and corresponding 95% CIs will be estimated using a Cox proportional hazards (CPH) model, with treatment group as a single covariate, stratified by the protocol-specified factors.

RFS curves will be estimated using Kaplan-Meier (K-M) product-limit methodology. Median RFS with 2-sided 95% CIs using the log-log transformation will be computed.

RFS rates at 12, 18, 24, and 36 months (and yearly after depending on follow-up) with 2-sided 95% CIs using the log-log transformation will be computed.

For RFS, a supplemental analysis will be performed using a while on study treatment estimand strategy to handle the intercurrent events of start of new anticancer therapy, tumor-directed radiotherapy, or tumor-directed surgery (excluding basal cell carcinoma [BCC]/squamous cell carcinoma [SCC] removal). Under this strategy, RFS will be censored on the date of last evaluable disease assessment prior to or on the same date of initiation of new anticancer therapy, tumor-directed radiotherapy, or tumor-directed surgery (excluding BCC/SCC removal).

For the supplemental descriptive analysis, the RFS curves will be estimated using Kaplan-Meier (K-M) product-limit methodology. Median RFS with 2-sided 95% CIs using the log-log transformation will be computed.

OS is defined as the time from randomization to the date of death from any cause. For participants that are alive (ie, without documentation of death), their survival time will be censored at the date of last contact date (or “last known alive date”). OS will be censored at the date of randomization for subjects who were randomized but had no follow-up. OS will be followed continuously while participants are on the study drug and every 3 months via in-person or phone contact after participants discontinue the study drug.

[figure not shown]
In Part 1 OS distributions will be descriptively compared between treatment groups, hazard ratio, and corresponding 95% CIs will be estimated using a CPH model, with treatment group as a single covariate, stratified by the protocol-specified factors.

OS curves will be estimated using K-M product-limit methodology. Median OS with 2-sided 95% CIs using the log-log transformation will be computed.

OS rates at 12, 18, 24, and 36 months with 2-sided 95% CIs using the log-log transformation will be computed.

All safety analyses will be performed using the All Treated participants population. Descriptive statistics of safety will be presented using NCI CTCAE v5 by treatment group. AEs will be coded using the most recent Medical Dictionary for Regulatory Activities (MedDRA) version available during the conduct of the study.

Frequency distribution of treated participants with AE using the worst CTC grade will be presented. Participants will only be counted (1) once at the preferred term (PT) level, (2) once at the system organ class (SOC) level, and (3) once in the “total participant” row at their worst CTCAE grade, regardless of SOC or PT.

10.4.4 *Exploratory Endpoint(s)*

Exploratory analyses will be described in the SAP that will be finalized before the database lock.

10.4.5 *Other Analyses*

10.4.5.1 *Exposure-Response Analyses*

Not applicable per Protocol Amendment 01. The following information refers to the original study design.

Model-determined nivolumab exposures may be used for exposure-response (E-R) analyses. If E-R analyses are conducted, the methods and results would be reported in a separate pharmacometrics report.

10.4.5.2 *Immunogenicity Analyses*

Not applicable per Protocol Amendment 01. The following information refers to the original study design.

All immunogenicity analyses will be performed using the Immunogenicity Evaluable Participants population.

A listing will be provided for all available immunogenicity data. A baseline ADA positive participant is defined as a participant with positive seroconversion detected in the last sample before initiation of treatment. An ADA-positive participant is a participant with at least 1 ADA-positive sample relative to baseline after initiation of the treatment. For each drug, frequency distribution of baseline ADA-positive participants and ADA-positive participants after initiation of the treatment will be summarized. To examine the potential relationship between

immunogenicity and safety, a table summarizing the frequency and type of AEs of special interest may be explored by immunogenicity status.

In addition, potential relationships between immunogenicity and efficacy and/or PK may also be explored.

10.4.5.3 *Outcomes Research*

Not applicable per Protocol Amendment 01. The following information refers to the original study design.

Unless otherwise specified in the SAP, the analysis of Outcome Research endpoints will be performed on the All Treated participants population and will be restricted to treated participants who have an assessment at baseline and at least 1 post-baseline assessment for the given questionnaire (where applicable). Descriptive statistics will be provided.

10.4.5.4 *Biomarkers*

Not applicable per Protocol Amendment 01. The following information refers to the original study design.

For biomarker participants, descriptive summary statistics of biomarker assessments will be presented at baseline and at each on-study time point described in [Section 9.8](#), unless otherwise specified.

[figure not shown]
10.4.6 *Study Analyses Timeframe*

The following DBLs will be performed:

10.4.6.1 *Part 1*

Not applicable per Protocol Amendment 01. The following information refers to the original study design.

Primary lock for Part 1 will be performed after all randomized participants in both arms have completed PK evaluation for the co-primary endpoints (Week 17). Subsequent database lock(s) will occur at 18 and 36 months after last participant is randomized (minimum follow-up of 18 and 36 months for all randomized participants) to assess for longer safety and efficacy secondary endpoint of RFS.

10.4.6.3 *Final Analysis*

The DBL will occur approximately 100 days after the last participant last treatment or earlier as applicable due to participant death or lost to follow-up.

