Nivolumab monotherapy was originally approved as a body weight-based dose of 3 mg/kg IV Q2W and was recently updated to flat-dosing regimens of 240 mg Q2W or 480 mg Q4W in multiple indications. For this study, the selected dose of 240 mg via IV Q2W is per dose/schedule approved for this patient population. In addition, there is extensive PK, safety, and efficacy data available at this dose across multiple tumors and dosing regimens. Global development with flat doses of nivolumab are ongoing in a broad range of clinical trials in a variety of additional tumor types. Based on the aforementioned nivolumab 240 mg IV Q2W is considered an appropriate and globally accepted comparator to [REDACTED]

In relation to transition to 480 mg IV Q4W, most recently, data from the comparator arm in study CA209915 support that the activity of flat dose (480 mg IV Q4W) nivolumab performs similarly to the originally assessed 3 mg/kg IV Q2W dosing schedule in study CA209238.

Additional details on nivolumab posologies and risk-benefit can be found in the BMS-936558 investigator brochure.

[REDACTED]

5.5.4 *Rationale for Switch from Q2W to Q4W (Arm B [IV])*

In order to mitigate participant burden, a switch from Q2W to Q4W will occur after Cycle 5 for participants in Arm B receiving IV nivolumab. Cycle 5 has been selected as the time for the switch as it was the time at which the primary endpoints in the original study design were being collected.

5.5.5 *Rationale for Continued Adjuvant Therapy for Participants Who Are Diagnosed with Melanoma in Situ During Study Treatment*

Malignant melanoma in situ (MMIS) Stage 0 includes Tis, N0, M0, demonstrates a radial growth phase in which the proliferation of malignant melanocytes is confined to the epidermis. Patients with a new Stage 0 melanoma are at minimal risk from that new tumor. The risk of death develops from advanced Stage IIIB/C/D or Stage IV melanoma for which they are receiving treatment during the clinical trial. Opdivo (nivolumab) is approved for the adjuvant treatment of adult patients with melanoma with involvement of lymph nodes or metastatic disease who have undergone complete resection. Consequently, in the absence of intolerable toxicity, patients with diagnosed MMIS should continue adjuvant therapy using the same dose and schedule for their original melanoma for a maximum of 1-year total duration starting from first dose (maximum of 13 doses). Melanoma in situ will not be considered a new primary malignancy.

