 - A subsequent scan not earlier than 4 weeks from the time when recurrence was first suspected demonstrates that the lesion size is \geq 5 mm over the size previously recorded, or the radiographic appearance of the lesion has become consistent with tumor recurrence. If this occurs, the date of recurrence will be the date when the lesion was first suspected.
 - Positive histology/cytology
- Appearance of multiple new lesions in the same time point generally constitutes unequivocal recurrence, even though they may be from different organs (eg, one liver lesion, one lung lesion, and one enlarged lymph node).

Criteria for Diagnosing Recurrences is presented in Table 9.1.3.2-1.

Table 9.1.3.2-1: Criteria for Diagnosing Recurrence

Anatomic Sites	Criteria
Non-Nodal Soft Tissue	
Equivocal lesions include:
 
 • Solitary lesion measuring $<$ 10 mm in LD or with radiographic appearance equivocal for tumor recurrence. 
Unequivocal lesions include:
 
 • One or more new lesions $>$ 10 mm in LD with radiographic appearance consistent with tumor recurrence. • Positive histology/cytology.
Bone Lesions	
Equivocal lesions include:
 
 • Solitary lesion. • Lesions identified on radionuclide bone scan. Findings on radionuclide bone scan must be confirmed by CT, MRI, or plain films in order to be upgraded to unequivocal. 
Unequivocal lesions include:
 
 • Two or more new lesions consistent with tumor recurrence. • Positive histology/cytology.
Lymph Nodes ^a	
Normal lymph nodes are defined as $<$ 10 mm in the SAD.
 
Equivocal lymph nodes include:
 
 • Lymph nodes measuring 10–14 mm SAD with radiographic appearance consistent with recurrence. • Lymph nodes \geq 15 mm SAD without radiographic appearance consistent with recurrence. 
Unequivocal proof of nodal recurrence includes:
 
 • One or more previously normal or equivocal lymph nodes that enlarge to \geq 15 mm SAD and with radiographic appearance consistent with recurrence. • Positive histology/cytology

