9.1.3.3 Definitions

Recurrence is defined as the appearance of one or more new melanoma lesions (except MMIS), which can be local, regional, or distant in location from the primary resected site.

Local Cutaneous Recurrence

Local recurrence is defined as tumor regrowth within 2 cm of the surgical incision following definitive excision of a primary melanoma with appropriate surgical margins. Lesions must be unequivocal. Local cutaneous recurrence after adequate excision of the primary melanoma is associated with aggressive tumor biologic features and is frequently a harbinger of metastases.

In Transit Metastasis Recurrence

Any skin or subcutaneous metastases more than 2 cm from the primary melanoma lesion, but not beyond the regional lymph node. When present, in transit metastases are usually multiple, evolve over time, and, as previously stated, are often the harbinger of subsequent systemic disease.

Regional Nodal Recurrences

Regional node failure, usually at the periphery of the prior surgical procedure. Lesions must be unequivocal as noted in [Table 9.1.3.2-1](#).

Distant Recurrence

Any distant metastases with radiographic appearance consistent with tumor recurrence or positive histology/cytology (typically defined as any M except for M0). Distant metastases include node relapses beyond the anatomical compartment of the primary melanoma basin, a nodal basin situated in a different anatomical compartment beyond the primary melanoma lesion, or in 2 nodal basins (even if contiguous; ie, 2 pelvic nodal basins, 2 mediastinal nodal basins, etc).

Considerations for establishing distant recurrence on cross-sectional imaging:

- CT and MRI are an important part of the work-up to establish recurrence. Contrast-enhanced CT and MRI are the preferred imaging modalities. See [Section 9.1.1](#) for details.
- Positron emission tomography (PET) alone will not be considered for the disease assessment. Complementary CT and/or MRI or biopsy must be performed in such cases.
- Cytology and/or histology are mandatory to confirm recurrence in solitary or in doubtful lesions, cutaneous, subcutaneous, or lymph node lesions. Histological or cytological evidence

of recurrence should be attempted in all cases (except for brain metastases) when safe and clinically feasible.

Clinically detected new lesions:

- The neoplastic nature of superficial cutaneous lesions must be confirmed by cytology/histology.

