9.1.3.4 Date of Recurrence

The first date when recurrence was observed is taken into account regardless of the method of assessment. Therefore, recurrence will be declared for any lesion when:

- Only imaging was performed and recurrence confirmed
- Only pathology was done and malignancy confirmed (in solitary or in doubtful lesions, cutaneous, subcutaneous, or lymph node lesions)
- Both pathology and imaging were done and recurrence/malignancy confirmed. In this case, the date of whichever examination comes first is considered the date of recurrence.

Pathology reports of biopsies confirming recurrence should be sent to a central vendor.

Note: For documentation, the date of recurrence is the date that the pathology and/or imaging confirms recurrence - not the date that the information was communicated to the participant.

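### Do the retained in situ wording in the RFS definition and the note on recurrence dates leave the RFS endpoint contradictory?

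*Combined protocol and SAP*

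**What the plan says.** **In situ disease.** Section 10.4.3.1 defines RFS from randomization to first recurrence, "new primary melanoma (including melanoma in situ), or death (whatever the cause), whichever occurs first". The matching row of Table 10.4.3.1-2 begins "Recurrence (local, regional, distant, new primary melanoma, including melanoma", adds the in situ qualifier, and gives the outcome as an event. Table 10.4.3.1-1 in the same section does not mention in situ disease: "date of first recurrence (local, regional, or distant metastasis), new primary melanoma, or death (whatever the cause), whichever occurs first". The section opens with "Not applicable per Protocol Amendment 01. The following information refers to the original study design".

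The amended text elsewhere differs. Section 9.1.3.3 has "Recurrence is defined as the appearance of one or more new melanoma lesions (except MMIS", and Section 5.5.5 has "Melanoma in situ will not be considered a new primary malignancy".

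**Dating.** For an equivocal lesion upgraded by a later scan, Section 9.1.3.2 says "If this occurs, the date of recurrence will be the date when the lesion was first suspected". The closing note of Section 9.1.3.4 says "the date of recurrence is the date that the pathology and/or imaging confirms recurrence", as opposed to the day the participant was told.

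**Status of RFS.** Table 4-1 lists RFS and 12-month OS as exploratory. The text above that table, and Section 10.4.3, say efficacy analyses will not be carried through. Section 10 nevertheless promises efficacy tables and listings for the study report. Section 10.4.4 places exploratory analyses in a SAP to be finalised before lock. The combined document holds no separate SAP text on RFS.

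**The concern.** On a first reading, a listed endpoint has one available definition, and that definition disagrees with the current recurrence rules. An analyst who took it up would score an RFS event at an in situ diagnosis and disregard any later true recurrence. The investigator, following Sections 9.1.3.3 and 5.5.5, would regard the same participant as free of recurrence and continue treatment. The derivation would also stall: RFS is to be programmed from the investigator's recurrence date, and no such date would exist for an in situ case.

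The dating rules raise a second doubt. Suppose a lesion is suspected at month 11.5 and confirmed by scan at month 12.5. It is an event by 12 months if dated to first suspicion, and event-free at 12 months if dated to confirmation. With arms of 6 and 8, one participant changes the estimate visibly.

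**Working it through.** The documents give no RFS estimate, event target or power figure, so there is nothing of the plan's own to reproduce beyond the count 6 + 8 = 14 (Section 5.2), which adds up.

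**1. Which in situ text is in force?**

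| Place | In situ rule | Status |
|---|---|---|
| 10.4.3.1, text and Table 10.4.3.1-2 | RFS event | Marked not applicable; original design |
| 9.1.3.3 | Not recurrence | Current |
| 5.5.5 | Not a new primary malignancy | Current; rationale for continuing therapy |

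The summary of changes records the Section 9.1.3.3 exclusion and the new Section 5.5.5 as intended amendments. Two live rules therefore do not collide. What is missing is an RFS definition in force.

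**2. Is the composite itself incoherent?** RFS is the time to the first of recurrence, new primary melanoma or death. A participant who dies without recurrence is already an RFS event with no recurrence. Disregarding later events is a property of any time-to-first-event endpoint. Section 9.1.3.3 defines recurrence, which is one component of RFS.

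**3. Size of the in situ choice.** Assume one in situ case, no other event, and no censoring before 12 months. The estimate is (n − k)/n with an exact (Clopper-Pearson) 95% interval, where k is 1 if the case counts and 0 if it does not.

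| Group | k = 0 | k = 1 | Shift |
|---|---|---|---|
| Arm A, n = 6 | 100% (54.1–100) | 83.3% (35.9–99.6) | 1/6 = 16.7 points |
| Arm B, n = 8 | 100% (63.1–100) | 87.5% (47.3–99.7) | 1/8 = 12.5 points |
| All, n = 14 | 100% (76.8–100) | 92.9% (66.1–99.8) | 1/14 = 7.1 points |

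The intervals overlap heavily.

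**4. Do the date rules conflict?**
- The opening sentence of Section 9.1.3.4 takes the first date on which recurrence was seen. When imaging and pathology were both done, the earlier examination counts. Both points fit Section 9.1.3.2.
- The note's stated contrast is between the examination date and the date of telling the participant.
- The backdating sentence in Section 9.1.3.2 is attached only to the route through a later scan. The histology/cytology route has no 4-week minimum and no stated backdating.
- A specific rule for scan-upgraded lesions beside a general note reads naturally as an exception.

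**5. Size of the date choice.** For a scan-upgraded lesion the gap is at least 4 × 7 = 28 days. If the confirming scan is the next 12-weekly one, the gap is 12 × 7 = 84 days, or 84 ± 14 = 70 to 98 days with ±7 days at each scan. The rules change when the event falls. They change 12-month status only if suspicion and confirmation lie on opposite sides of 12 months.

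**The case for a change.** The strongest case for a change is that RFS is not dead. It stands in the amended Table 4-1, Section 10 promises efficacy summaries, Section 10.3 names the dataset for efficacy, and Section 9.1.3.2 keeps a censoring rule for non-melanoma cancers that makes sense only for an endpoint such as RFS. The one definition the SAP could inherit was not brought into line with the amended in situ rule, and a few sentences before lock would settle it.

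The date problem sits wholly in live text, and the recommended schedule could produce it. Scans at weeks 48 and 60 fall near days 1 + 48 × 7 = 337 and 1 + 60 × 7 = 421, on either side of 12 months. In Arm B a last dose on Cycle 13 Day 1 (day 337) carries follow-up to 337 + 100 = day 437, so the second scan can fall inside it.

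Two parts of this stand. RFS has no definition in force, and the Section 9.1.3.4 note, taken alone, can be read against Section 9.1.3.2. The rest does not carry. The SAP is the stated home for exploratory analyses, and its author will see both the label on Section 10.4.3.1 and the amended rules. Nothing obliges that author to reuse the old definition. The straddling case also needs an equivocal lesion at one particular scan, upgraded at the next, in a study that allows local imaging schedules.

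**Conclusion.** No change to the plan is called for. The in situ difference is between labelled original-design text and a deliberate amendment. The remaining gap is ordinary detail for the SAP: whether RFS is reported at all, given the statements that efficacy analyses will not be completed, and if so how in situ disease counts.

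Striking in situ disease from the composite would not be a plain gain. Statisticians differ on whether an in situ second primary belongs in RFS. Section 10 also foresees summaries on the original study objectives, for which the original definition may be wanted, and removing it would cost comparability. With 14 participants and efficacy listings planned, any in situ case could be shown individually under either choice.

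The dating point is a loosely worded note that analysts would read beside the scan-upgrade rule. Its effect is at least 28 days for scan-upgraded lesions, and on 12-month status only across the landmark.

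This rests on the SAP being finalised before lock, as Sections 10.4 and 10.4.4 state, and on RFS remaining exploratory and descriptive. The shifts of 16.7 and 12.5 points are hypothetical: the documents report no in situ case. No hypothesis test or decision depends on them.
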